## Appendix 3: Adverse Events: Definitions and Procedures for Recording, Evaluating, Follow-Up, and Reporting

---

### A3–7.6 ABNORMAL VITAL SIGN VALUES

Not every abnormal vital sign value qualifies as an adverse event. A vital sign abnormality that is associated with the underlying disease should not be reported as an adverse event unless judged by the investigator to be more severe than expected. A vital sign abnormality that is not associated with the underlying disease must be reported as an adverse event if it meets any of the following criteria:

- Is accompanied by clinical symptoms
- Results in a change in study treatment (e.g., dose modification, treatment interruption, or treatment discontinuation)
- Results in a medical intervention or a change in concomitant therapy
- Is clinically significant in the investigator's judgment

It is the investigator's responsibility to review all vital sign findings. Medical and scientific judgment should be exercised in deciding whether an isolated vital sign abnormality should be classified as an adverse event.

If a clinically significant vital sign abnormality is a sign of a disease or syndrome (e.g., high blood pressure), only the diagnosis (e.g., hypertension) should be recorded on the Adverse Event eCRF.

Observations of the same clinically significant vital sign abnormality from visit to visit should only be recorded once on the Adverse Event eCRF (see Section [A3–7.4](#) for details on recording persistent adverse events).

### A3–7.7 ABNORMAL LIVER FUNCTION TESTS

The finding of an elevated ALT or AST ( $>3 \times \text{ULN}$ ) in combination with either an elevated total bilirubin ( $>2 \times \text{ULN}$ ) or clinical jaundice in the absence of cholestasis or other causes of hyperbilirubinemia is considered to be an indicator of severe liver injury (as defined by Hy's Law). Therefore, investigators must report as an adverse event the occurrence of either of the following:

- Treatment-emergent ALT or AST  $>3 \times \text{ULN}$  in combination with total bilirubin  $>2 \times \text{ULN}$
- Treatment-emergent ALT or AST  $>3 \times \text{ULN}$  in combination with clinical jaundice

The most appropriate diagnosis or (if a diagnosis cannot be established) the abnormal laboratory values should be recorded on the Adverse Event eCRF (see Section [A3–7.2](#)) and reported to the Sponsor immediately (i.e., no more than 24 hours after the investigator becomes aware of the event), either as a serious adverse event or an adverse event of special interest (see Section [A3–5](#)).

## Appendix 3: Adverse Events: Definitions and Procedures for Recording, Evaluating, Follow-Up, and Reporting

---

### A3-7.8 DEATHS

For this protocol, mortality is an efficacy endpoint. Deaths that occur during the protocol-specified adverse event reporting period (see Section [8.3.1](#)) that are attributed by the investigator solely to progression of SCLC should be recorded on the Death Attributed to Progressive Disease eCRF. All other deaths that occur during the adverse event reporting period, regardless of relationship to study treatment, must be recorded on the Adverse Event eCRF and immediately reported to the Sponsor (see Section [A3-5](#)). An independent monitoring committee will monitor the frequency of deaths from all causes.

Death should be considered an outcome and not a distinct event. The event or condition that caused or contributed to the fatal outcome should be recorded as the single medical concept on the Adverse Event eCRF. Generally, only 1 such event should be reported. If the cause of death is unknown and cannot be ascertained at the time of reporting, "**unexplained death**" should be recorded on the Adverse Event eCRF. If the cause of death later becomes available (e.g., after autopsy), "unexplained death" should be replaced by the established cause of death. The term "**sudden death**" should not be used unless combined with the presumed cause of death (e.g., "sudden cardiac death").

Deaths not related to progression of the underlying cancer and occurring within the adverse event reporting period, must be reported as serious adverse event, regardless of relationship to study treatment. Deaths not related to progression of the underlying cancer and occurring outside the adverse event reporting period should only be reported as serious adverse event if considered related to prior exposure to study treatment. Deaths not related to progression of the underlying cancer and outside the adverse event reporting period and considered unrelated to prior exposure to study treatment should be reported through use of the Long-Term Follow-Up eCRF. Deaths related to the progression of the underlying cancer occurring during the adverse event reporting period should be reported on the Death Attributed to Progressive Disease eCRF. Deaths related to the progression of the underlying cancer occurring outside the adverse event reporting period should be reported on the Long-Term Follow-Up eCRF (for an overview, see [Table A3-3](#)).

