4.3.5 Incidence and Severity of Adverse Events

The secondary safety objective will be assessed through summaries of the incidence and severity of treatment-emergent adverse events (AEs) in the SAS.

Verbatim description of adverse events will be mapped to the Medical Dictionary for Regulatory Activities (MedDRA) thesaurus terms. Severity for all adverse events will be graded by the investigator according to the National Cancer Institute Common Terminology Criteria for Adverse Events (NCI CTCAE) v5.0. Severity for Cytokine release syndrome (CRS) will also be graded by the investigator according to the American Society of Transplantation and Cellular Therapy (ASTCT) consensus grading scale. All adverse events will be summarized by treatment arm and NCI CTCAE grade. Cytokine release syndrome will also be summarized by treatment arm and the ASTCT consensus grade. All adverse events, Grade 3-4 adverse events, serious adverse events, adverse events leading to death, adverse events of special interest, adverse events leading to treatment interruption/modification and adverse events leading to study treatment discontinuation that occur on or after the first dose of study treatment (i.e., treatment-emergent adverse events) will be summarized by preferred term, system organ class, and severity grade. For events of varying severity, the highest grade will be used in the summaries. Multiple occurrences of the same event in the same patient will

be counted once at the maximum severity. Deaths and cause of death will be summarized.

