4.3.6 Time to Confirmed Deterioration

Confirmed clinically meaningful deterioration for physical functioning and Global Health Status (GHS)/Quality of Life (QoL) is defined as a clinically meaningful decrease from baseline in the physical functioning or GHS/QoL scores that must be held for at least two consecutive assessments or an initial clinically meaningful decrease above baseline followed by death attributable to cancer progression within 6 weeks of the last deteriorated PRO assessment. A score change of \geq 10-point change in GHS/QoL and functional subscale scores is perceived by participants as clinically meaningful (Osoba et al. 1998).

For time to confirmed deterioration (TTCD), data for participants will be censored at the last time when they completed an assessment if they have not experienced a confirmed clinically meaningful deterioration at the clinical cutoff date. If no baseline or post-baseline assessment is performed, participants will be censored at the randomization date. According to the while-on-treatment/while-alive strategy, participants who die before reporting any clinically meaningful deterioration will be censored at the last time they completed an assessment. Time to confirmed deterioration using the European Organization for Research and Treatment of Cancer (EORTC) scale will be analyzed with use of the same methods as for PFS.

[REDACTED]

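### Protocol A3-7.8 gives two different criteria for recording a death with mixed causes, so whether it counts as a fatal adverse event depends on which paragraph the site follows

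*Protocol*

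**What the plan says.** Protocol A3-7.8 (Deaths) has three paragraphs.

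- **Paragraph 1** covers deaths in the adverse event reporting period "that are attributed by the investigator solely to progression of SCLC should be recorded on the Death Attributed to Progressive Disease eCRF". It continues: "All other deaths that occur during the adverse event reporting period, regardless of relationship to study treatment, must be recorded on the Adverse Event eCRF", with immediate reporting to the Sponsor.
- **Paragraph 2** treats death as an outcome and says: "The event or condition that caused or contributed to the fatal outcome should be recorded as the single medical concept on the Adverse Event eCRF".
- **Paragraph 3** divides deaths in the same period by relation to progression. On one side: "Deaths not related to progression of the underlying cancer and occurring within the adverse event reporting period, must be reported as serious adverse event". On the other: "Deaths related to the progression of the underlying cancer occurring during the adverse event reporting period should be reported on" the progressive-disease form. The qualifier *solely* does not appear.

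Table A3-3, offered as the overview, has three cause rows: SCLC, unrelated Grade 5 adverse event, and related Grade 5 adverse event. It has no mixed-cause row and does not say whether SCLC must be the only cause.

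SAP 4.3.5 summarises "adverse events leading to death" by treatment arm in the safety analysis set, as part of the secondary safety objective. Deaths and causes of death are also summarised there.

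**The concern.** *Attributed solely to* and *related to* are different thresholds applied to the same deaths in the same period. They disagree for a death to which both progression and another event contributed, for example an infection during neutropenia in a participant whose disease is progressing.

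Two sites, or one site on two occasions, could follow the protocol and record such a death differently. That would change three things:

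- whether the contributing event carries a fatal (Grade 5) outcome;
- whether the death itself triggers an immediate report;
- whether the participant enters the by-arm count of fatal adverse events.

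The investigator assigns the cause, and the trial is open-label. Arm A adds a myelosuppressive drug: Protocol A6-1.1.1 gives Grade 3/4 neutropenia in 40.8% and treatment-related febrile neutropenia in 6.5% of participants on single-agent lurbinectedin at the study dose. So both the number of mixed-cause deaths and the way they are attributed could differ between arms, although the documents do not show that they do.

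**Working it through.** The plan states no figure on this point, so the main check is textual. Take a death in the reporting period, which Table A3-3 (note a) defines as up to 90 days after the final dose or until new systemic anti-cancer therapy starts, whichever is first. Trace it through each rule.

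| Cause of death | Paragraphs 1 and 2 | Paragraph 3 | Agree? |
|---|---|---|---|
| Progression only | Progressive-disease form | Progressive-disease form | Yes |
| Unrelated to progression | Adverse Event eCRF, immediate report | Serious adverse event | Yes |
| Progression and another contributing event | Adverse Event eCRF, immediate report; contributing event recorded as the fatal concept | Progressive-disease form; outside the serious adverse event rule for deaths | **No** |

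Next, does any other text resolve the third row?

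- Table A3-3: a mixed-cause death could be placed in the SCLC row or in a Grade 5 row, and these lead to different forms.
- A3-2 says that death due to progression is not a serious adverse event. It does not address shared causes.
- Paragraph 3 does not forbid completing an Adverse Event eCRF as well, but neither it nor the table asks for one.

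Finally, what can be said about size? SAP 2.2.3 gives a target of 450 randomised participants, and allocation is 1:1, so 450 / 2 = 225 per arm (the safety analysis set may be slightly smaller). Let m_A and m_B be the numbers of mixed-cause deaths in the period.

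- Largest change in one arm's fatal adverse event rate = m / 225. For one death, 1 / 225 = 0.44 percentage points.
- Change in the difference between arms, if all such deaths move = (m_A − m_B) / 225. If m_A = m_B, this is 0.

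The documents give neither m_A nor m_B, nor a share from which to derive them.

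**The case against.** The strongest reply is that most of the text already points one way. Paragraphs 1 and 2 both put a mixed-cause death on the Adverse Event eCRF. Table A3-1 defines Grade 5 as death related to an adverse event, so such a death fits the Grade 5 rows of Table A3-3. Section A3-7.11 also uses a sole-cause test when it exempts hospitalisation for progression. On this view paragraph 3 is loosely worded. That is a fair account of the likely intent, and it is a reason to adopt paragraph 1's criterion. It does not remove the conflict, because paragraph 3 is also an operative rule and the table does not overrule it.

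Three stronger readings are tempting, and the documents do not support them.

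- **That the event drops out of the safety data under paragraph 3.** It does not. Section 8.3.1 requires all adverse events to be reported to 30 days, and serious events to 90 days, after the final dose, unless new systemic therapy starts first. A3-7.3 requires neutropenia and an accompanying infection to be recorded separately. A3-2 and the notes to Table A3-1 make life-threatening or hospitalising events serious. A contributing sepsis stays reportable; its fatal outcome is what may be lost.
- **That the choice of form changes time to confirmed deterioration.** SAP 4.3.6 counts an initial deterioration "followed by death attributable to cancer progression within 6 weeks" of the last deteriorated assessment. Nothing in the SAP says that this attribution is taken from the progressive-disease form.
- **That the effect is large.** Suppose 20% of an arm died in the period and 5% to 20% of those deaths were mixed. The arm's rate would move by 0.20 × 0.05 = 1 point to 0.20 × 0.20 = 4 points. Both shares are assumptions, and with equal shares in the two arms the contrast would not move. A by-arm effect needs a difference in mixed-cause deaths or in how they are attributed, and the documents give no figure for either.

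**Conclusion.** The inconsistency is real and sits within one section: a mixed-cause death in the reporting period is a fatal adverse event under paragraphs 1 and 2 of A3-7.8 and not under paragraph 3. This is a conflict between two stated rules, which goes beyond missing detail.

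The consequence is limited to the fatal-outcome flag, the death-triggered immediate report, and the by-arm summaries that use them. OS and PFS count death from any cause and are unaffected. All deaths are summarised in any case, and a monitoring committee follows deaths from all causes.

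The size cannot be estimated beyond about 0.44 points in an arm's rate per reclassified death, assuming 225 per arm. The conclusion assumes no completion guideline outside these documents that already settles mixed-cause deaths. It is worth correcting because the affected table is a secondary safety output that rests on open-label attribution, and the correction is nearly free.

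**What to change.** Use paragraph 1's criterion throughout A3-7.8.

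- In paragraph 3, replace *not related to progression* with *not attributed solely to progression*, and *related to the progression* with *attributed solely to the progression*, at each occurrence.
- In Table A3-3, relabel the row *SCLC* as *SCLC as sole cause*. Mixed-cause deaths in the reporting period then go on the Adverse Event eCRF.

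The rationale for Version 8 says that the cutoff for the final OS analysis has been reached and that some analyses are complete, so the rewording helps only deaths still to be recorded. If existing records are checked, the check should cover deaths on both forms in both arms, be done without sight of treatment arm, and be able to reclassify in either direction. A query confined to progressive-disease-form deaths with a concurrent Grade 3-4 event should be avoided: it could only add fatal adverse events, and it would draw more cases from the arm with more Grade 3-4 toxicity.

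The cost is a wording change, a small data-query workload if the check is done, and a possible small change in the reported fatal adverse event count.

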**Appendix 3: Adverse Events: Definitions and Procedures for Recording, Evaluating, Follow-Up, and Reporting**

---

**Table A3-3 Documentation Required for Reporting Deaths**

Cause of Death	Timing	
	During Adverse Event Reporting Period a	After Adverse Event Reporting Period
SCLC	Death Attributed to Progressive Disease eCRF	Long-Term Follow-Up eCRF
Unrelated Grade 5 Adverse Event	Adverse Event eCRF	Long-Term Follow-Up eCRF b
Related Grade 5 Adverse Event	Adverse Event eCRF	Adverse Event eCRF c

eCRF=electronic Case Report Form; EDC=electronic data capture; SCLC=small-cell lung cancer.

- a Up to 90 days after final dose of study treatment or until start of new systemic anti-cancer therapy, whichever occurs first.
- b Record the primary cause of death as "other", for "other death cause" specify the Adverse Event term.
- c If the EDC system is not available, the investigator should report these events directly to the Sponsor or its designee, either by faxing or by scanning and e-mailing the paper Clinical Trial Adverse Event/Special Situations Form using the fax number or e-mail address provided to investigators.

**A3-7.9 PREEXISTING MEDICAL CONDITIONS**

A preexisting medical condition is one that is present at the screening visit for this study. Such conditions should be recorded on the General Medical History and Baseline Conditions eCRF.

A preexisting medical condition should be recorded as an adverse event only if the frequency, severity, or character of the condition worsens during the study.

When recording such events on the Adverse Event eCRF, it is important to convey the concept that the preexisting condition has changed by including applicable descriptors (e.g., "more frequent headaches").

**A3-7.10 LACK OF EFFICACY OR WORSENING OF SCLC**

Medical occurrences or symptoms of deterioration that are anticipated as part of SCLC should not be recorded as adverse events. However, deterioration that is judged by the investigator to have unexpectedly worsened in severity or frequency or changed in nature at any time during the study should be recorded as an adverse event.

When recording an unanticipated worsening of SCLC on the Adverse Event eCRF, it is important to convey the concept that the condition has changed by including applicable descriptors (e.g., "accelerated worsening of small-cell carcinoma").

---

### Appendix 3: Adverse Events: Definitions and Procedures for Recording, Evaluating, Follow-Up, and Reporting

---

#### **A3–7.11 HOSPITALIZATION OR PROLONGED HOSPITALIZATION**

Any adverse event that results in hospitalization (i.e., inpatient admission to a hospital) or prolonged hospitalization should be documented and reported as a serious adverse event (per the definition of serious adverse event in Section [A3–2](#)), except as outlined below.

An event that leads to hospitalization under the following circumstances should not be reported as an adverse event or a serious adverse event:

- Hospitalization for respite care
- Planned hospitalization required by the protocol (e.g., for study treatment administration or performance of a tumor assessment for the study)
- Hospitalization for a preexisting condition, provided that all of the following criteria are met:
  - The participant was hospitalized for an elective procedure that was planned prior to the study, was scheduled during the study despite the fact that the condition had not worsened, or was scheduled during the study when treatment became necessary because of the expected normal progression of the condition
  - The participant has not experienced an adverse event
- Hospitalization due solely to progression of the underlying cancer

An event that leads to hospitalization under the following circumstances is not considered to be a serious adverse event, but should be reported as an adverse event instead:

- Hospitalization that was necessary because of participant requirement for outpatient care outside of normal outpatient clinic operating hours

#### **A3–7.12 CASES OF ACCIDENTAL OVERDOSE OR MEDICATION ERROR**

Accidental overdose and medication error (hereafter collectively referred to as "special situations") are defined as follows:

- Accidental overdose: accidental administration of a drug in a quantity that is higher than the assigned dose
- Medication error: accidental deviation in the administration of a drug

In some cases, a medication error may be intercepted prior to administration of the drug.

### **Appendix 3: Adverse Events: Definitions and Procedures for Recording, Evaluating, Follow-Up, and Reporting**

---

Each adverse event associated with a special situation should be recorded separately on the Adverse Event eCRF. If the associated adverse event fulfills seriousness criteria or qualifies as an adverse event of special interest, the event should be reported to the Sponsor immediately (i.e., no more than 24 hours after the investigator becomes aware of the event; see Section [A3–5](#)). For lurbinectedin and atezolizumab, adverse events associated with special situations should be recorded as described below for each situation:

- Medication error that does not qualify as an overdose: Enter the adverse event term. Check the "Medication error" box.
- Medication error that qualifies as an overdose: Enter the adverse event term. Check the "Accidental overdose" and "Medication error" boxes.

As an example, an accidental overdose that resulted in a headache would require 2 entries on the Adverse Event eCRF, 1 entry to report the accidental overdose and 1 entry to report the headache. The "Accidental overdose" and "Medication error" boxes would need to be checked for both entries.

All special situations associated with lurbinectedin and atezolizumab, regardless of whether they result in an adverse event, should be recorded on the Adverse Event eCRF as described below:

- Accidental overdose: Enter the drug name and "accidental overdose" as the event term. Check the "Accidental overdose" and "Medication error" boxes.
- Medication error that does not qualify as an overdose: Enter the name of the drug administered and a description of the error (e.g., wrong dose administered, wrong dosing schedule, incorrect route of administration, wrong drug, expired drug administered) as the event term. Check the "Medication error" box.
- Medication error that qualifies as an overdose: Enter the name of the drug and "accidental overdose" as the event term. Check the "Accidental overdose" and "Medication error" boxes. Enter a description of the error in the additional case details.
- Intercepted medication error: Enter the name of the drug and "intercepted medication error" as the event term. Check the "Medication error" box. Enter a description of the error in the additional case details.

**Appendix 3: Adverse Events: Definitions and Procedures for Recording, Evaluating, Follow-Up, and Reporting**

---

**A3–7.13 PATIENT-REPORTED OUTCOME DATA**

Adverse event reports will not be derived from the Patient-Reported Outcomes Common Terminology Criteria for Adverse Events (PRO-CTCAE) or other PRO data by the Sponsor. In addition, the Sponsor will make no attempt to reconcile participant reports of treatment-related symptoms (via the PRO-CTCAE) with investigator reports of adverse events. Sites are not expected to review the PRO-CTCAE or other PRO data for adverse events.

[REDACTED]

[REDACTED]

[REDACTED]

